6.2 Rationale for the study

6.2.1 Muscarinic Cholinergic Receptors (CHRM₅)

Muscarinic cholinergic receptors (CHRM₅) are a family of seven-transmembrane domain receptors consisting of five receptor subtypes (M1-5) and are associated with heterotrimeric G-proteins to translate a transduction cascade (Bonner et al., 1987, Hulme et al., 1990). M1 and 3 receptors act as postsynaptic receptors in the central nervous system (CNS), where they are mainly localized in the cortex and hippocampus and play an important role in cognitive function (Porter et al., 2002). M2 and M4 receptors have been demonstrated to act as presynaptic autoreceptors in the cerebral cortex (Lai et al., 2001), basal ganglia and hippocampus (Lai et al., 2001; Dean et al., 2000; Scarr et al., 2007), having an inhibitory effect on the release of acetylcholine (Ach). M5 receptors are predominantly distributed in the hippocampus and substantia nigra and have been demonstrated to have a role in the modulation of dopamine release (Vilaro et al., 1990; Weiner et al., 1990).

6.2.2 Cholinergic System and Mood Disorders

Despite the paucity of human studies targeting the cholinergic system in mood disorders, this system has long been implicated as a contributory factor in their aetiology. In 1950, the organophosphorus insecticide disopropyl-fluorophosphate (DFP), a cholinesterase inhibitor (increasing synaptic ACh) was demonstrated to have a depressive effect on healthy controls and individuals with mania (Rowntree et al., 1950), with these findings also noted by other authors (Gershon and Shaw, 1961). Physostigmine, a cholinesterase inhibitor (and thus an opposite effect to Scopolamine) has been demonstrated to exacerbate depressive symptomatology in individuals with bipolar disorder (Davis et al., 1978; Janowsky et al., 1972). These, and other observations, have led to the hypothesis that an imbalance between central

cholinergic and adrenergic neurotransmitter activity, released from the cholinergic nerves in the parasympathetic, and adrenergic nerves in the sympathetic systems could induce mania and depression (Janowsky et al., 1972). Thus, over-activity and oversensitivity of the cholinergic system has been associated with depressive symptomatology, with a reduction in M2 receptors demonstrated *in vivo* during depression (Cannon et al., 2006), partially explained by variation in the M2 gene (Cannon et al., 2011). M2 antagonism by Scopolamine (a cholinergic antagonist) may potentially regulate activity of this system and therefore reduce the oversensitivity associated with depression.

6.2.3 Other proposed mechanisms for Scopolamine's putative antidepressant effect

In addition to modulation of the cholinergic system, several other potential mechanisms have been considered to explain the observed antidepressant effect of Scopolamine. This is likely given the persistence of the antidepressant effect beyond the plasma half-life of Scopolamine ($t_{1/2} = \sim 3$ hours) (Drevets and Furey, 2010). These include modulation of N-methyl-D-aspartate (NMDA) receptor activity, with increased NMDA receptor gene expression and reduced mRNA concentrations of NMDA receptors 1A and 2A in rodents' brain (Liu et al., 2004) resulting in reduced neuronal damage in the hippocampus secondary to glutamate mediated neurotoxicity (Rami et al., 1997). Further evidence for modulation of the glutamatergic system is derived from the enhancement of extracellular glutamate concentrations in the striatum in rodents with Scopolamine administration (Rawls and McGinty, 1988) which may additionally activate synaptic plastic pathways. Activation of synaptic plasticity has been proposed as an underlying biological effect for "scopolamine's rapid antidepressant activity, with scopolamine rapidly increasing mammalian target of rapamycin (mTOR) signalling and synaptogenesis (Voleti et al., 2013), with pre-treatment with mTOR and α -amino-3-hydroxy-5-methyl-4-isoxazolepropionic acid (AMPA) antagonists in animal trials (Voleti et al., 2013) blocking "Scopolamine's antidepressant effects. The mTOR pathway has similarly been implicated in the rapid antidepressant effects of ketamine (Dwyer et al., 2012).

6.2.4 Scopolamine administration in study

At Visit 2, all participants will receive placebo run-in (100mls of Saline IV) (see section 8.1.3 for rationale). The screening visit (Visit 1) and Visit 2 may occur on the same day. Within 7 days of Visit 2, participants will be randomised (Visit 3) to receive either placebo (n=25) or 4 μ g/kg Scopolamine (n=25) IV in 100mls of Saline over 15 minutes at Visits 3 (day 0), 4 (days 2-6) and 5 (days 6-10), with at least 2 days between IV infusions (Visits 2, 3, 4 and 5). Two follow-up visits (Visits 6 and 7) will occur at day 15 (+/- 5 days) and day 29 (+/- 7 days). There will be at least 2 days between Visits 5 and 6 and 3 days between Visits 6 and 7.

7. Study Objectives

7.1 Primary Objective

The primary objective is to investigate the efficacy and safety of IV Scopolamine, compared to placebo, in reducing severity of depression in individuals with bipolar disorder who are experiencing a depressive episode of at least moderate severity.

7.2 Secondary Objectives

There are a number of secondary objectives.

1. To investigate if IV Scopolamine compared to placebo improves mood, cognition and functioning as measured on a number of objective and subjective psychometric instruments in individuals with bipolar disorder experiencing a depressive episode of at least moderate severity.

2. To investigate the safety and tolerability of repeated (x3) IV Scopolamine versus placebo in individuals with bipolar disorder experiencing a depressive episode of at least moderate severity.

7.3 Primary and Secondary/exploratory endpoints/outcome measures

7.3.1 Primary Endpoint

The primary endpoint will be the change in severity of objective depressive symptoms as measured by change in HDRS score from pre-randomisation (pre-IV infusion on Visit 3) compared to Visit 6.

7.3.2 Secondary Endpoints

1. Remission of depressive episode measured with the HDRS at Visit 6 compared to Visit 3.
2. Response to a depressive episode measured with the HDRS at Visit 6 compared to Visit 3.
3. Reduction of depressive symptoms (MADRS) at Visit 6 compared to Visit 3.
4. Improvement in objectively measured overall functioning (GAF) at Visit 6 compared to Visit 3.
5. Reduction in depressive symptoms as measured using the POMS after all IV infusion visits compared to before IV infusions at the same visit (Visits 2, 3, 4, 5).
6. Response and remission data measured with the HDRS at Visit 7 compared to pre-randomisation HDRS scores at Visit 3.
7. Reduction in subjectively measured mood symptoms using the POMS at follow-up visits (Visits 6 and 7) compared to pre-randomisation.
8. Reduction in depressive symptoms, measured with the MADRS at Visit 7 compared to MADRS scores at Visit 3.
9. Improvement in global functioning, measured with the GAF at Visit 7 compared to pre-infusion GAF scores at Visit 3.
10. Psychiatric inpatient admissions due to depressive episodes over the duration of the study.
11. Antidepressant medication usage or change in antidepressant medication dose due to depressive episodes over the duration of the study.
12. Adverse events over the duration of the study.
13. Post infusion side effects at all 3 IV treatment visits: Bradycardia, Hypotension, Dizziness and Sedation (Visits 3, 4 and 5)
14. Occurrence of a hypo (manic) episode over the duration of the study.
15. Improvement in motor processing, visual and spatial memory at Visit 6 compared to initial scores measured at Visit 2 or Visit 3 as measured on CANTAB.

8. Trial Design

8.1 Design Summary

This is a single-site, randomised, double-blind, placebo-controlled, parallel, phase IIb clinical trial. The trial will be sponsored by the National University of Ireland (NUI) Galway and the sponsorship role coordinated by the HRB-Clinical Research facility Galway (CRFG).

The site will be University Hospital Galway, Galway and the site activities will also be coordinated by the CRFG. Participants will be attending the Galway-Roscommon Mental Health Services, including a specialised bipolar clinic in Galway and referred due to experiencing a depressive episode by their treating clinical team; or patients who have previously attended NUI Galway/HRB-CRFG with an interest to participate/or have

participated in research and have indicated a willingness to engage in future research; or patients who approach the research group directly requesting participation.

Once participants have consented to the trial they will be reviewed against the inclusion and exclusion criteria at the screening visit (Visit 1). Eligible participants will be randomised to one of two groups; treatment group ($n \sim 25$) or placebo group ($n \sim 25$). Participants will receive Scopolamine or placebo in addition to their current treatment regimen.

At the next visit, Visit 2, all participants will receive placebo run-in (100mls of Saline IV). This has been utilised in other IV Scopolamine treatment studies (Furey & Drevets, 2006; Drevets and Furey, 2010; Furey et al., 2010; Ellis et al., 2014) and has the advantage of reducing the subsequent placebo effect (when receiving active intervention) noted between groups and reducing the loss to follow-up rate post-randomisation (Davis et al., 1995; Rosenkranz, 2016).

The maximum time between screening (Visit 1) and Visit 2 is 14 days. The screening visit and Visit 2 can occur on the same day and thus some data attained on the 'screening visit' will not require replication on the same day including a review of inclusion and exclusion criteria, the Hamilton Depression Rating Scale (HDRS) and the Young Mania Rating Scale (YMRS) and pre-infusion vital signs.

Within 7 days of Visit 2, participants will be assessed against the placebo run-in criteria and if these criteria are met they will be randomised (visit 3) to receive either placebo ($n=25$) or 4 μ g/kg Scopolamine ($n=25$) IV in 100mls of Saline over 15 minutes at:

- Visit 3 (Day 0),
- Visit 4 (days 2-6) and
- Visit 5 (days 6-10),

At least two days will elapse between IV infusions (Visits 2-5).

Two follow-up visits (Visits 6 and 7) will occur at days 15 (+/-5 days) and days 29 (+/- 7 days).

At least two days will elapse between Visits 5 and 6.

8.1.1 Treatment Group

Participants randomised to the scopolamine group will receive one 15-minute infusion of IV Scopolamine in 100ml saline, repeated over 3 visits (Visit 3, 4 & 5).

[figure not shown]
8.1.2 Placebo Group

Participants randomised to the placebo group will receive one 15-minute infusion of IV saline, repeated over 3 visits (Visit 3, 4 & 5).

8.1.3 Placebo run-in

All participants will receive placebo at Visit 2, known as a placebo run-in. In addition, at Visit 3 pre-randomisation, participants must ensure they continue to fulfil placebo run-in inclusion criteria.

Figure 1: CONSORT Trial Flow Diagram: A Randomised Double-Blind Placebo-Controlled Trial of Scopolamine in Bipolar Disorder

Note timeline between visits:

Visit 1 and 2: ≤14 days. Can also occur on the same day and thus data from screening visit does not need to be replicated at Visit 2.

Visit 2 and 3: ≥2 days and ≤7 days

Visit 3 and Visit 4 and Visit 5 and Visit 6: ≥2 days

Visit 6 and Visit 7: ≥3 days

8.2 Selection of study population

8.2.1 Population

There will be 50 adult trial participants (both male and female) who have bipolar disorder (bipolar disorder 1 or 2) and are experiencing a depressive episode of at least moderate severity as measured by a HDRS of ≥ 14 at Visit 2; with 25 participants randomised to receive Scopolamine and 25 randomised to receive placebo. It is anticipated that approximately 60 individuals will be recruited into the study at Visit 2, and that approximately 10 individuals will withdraw prior to study randomisation. Thus, the target for recruitment is approximately 60 patients with 50 patients to be randomised into the trial.

8.2.2 Inclusion criteria

To be eligible for inclusion, each participant must meet all of the following inclusion criteria at Screening (Visit 1) and must continue to fulfil these criteria at Visit 2 to take part in the trial:

1. Diagnosis of Bipolar Disorder according to Diagnostic Statistics Manual (DSM)-V criteria
2. Experiencing an episode of depression of at least moderate severity at Visit 1 (Screening) and Visit 2 based on clinical interview by a trained clinician and a Hamilton Depression Rating Scale (HDRS) score ≥ 14 .
3. ≥ 18 years old at Visit 2 (male or female)
4. In the opinion of the Principal Investigator or Sub Investigator's, be able and willing to provide written informed consent and to comply with the requirements of this study protocol.
5. Written informed consent prior to participating in the study
6. U&Es, LFTs and TFTs laboratory tests within acceptable ranges in the previous 4 months of the Screening Visit (Visit 1).

Placebo run-in inclusion criteria at Randomisation visit (Visit 3):

7. In addition to above, participants must be experiencing an episode of depression of at least mild severity (having previously experienced an episode of moderate depression at Visit 2 with HDRS ≥ 14), based on clinical interview by a trained clinician and a HDRS score of ≥ 8 .

8.2.3 Exclusion criteria

Participants who meet any one or more of the following exclusion criteria at Screening (Visit 1) or the Visit 2 will not be eligible to take part in the trial:

1. History of other Axis I diagnosis (including Recurrent Depressive Disorder or Psychotic Disorders such as schizo-affective disorder, conditions that can also present with depressive episodes)
2. History in the three months prior to Visit 2 of alcohol dependence syndrome or substance dependence syndrome.
3. Current use of oral steroid at Visit 1
4. A confirmed diagnosis of dementia
5. A diagnosis of intellectual disability (IQ < 70)
6. Participants with bipolar disorder that are euthymic in the investigators opinion at screening or Visit 2.

7. Participants with bipolar disorder that are hypomanic or manic (Young Mania Rating Scale (YMRS) > 6) at screening or Visit 2.
8. Presence of an established neurological disorder or other serious demyelinating conditions as determined by the treating physician (e.g. space occupying lesion, multiple sclerosis)
9. Current involuntary detention under the Mental Health Act (MHA) 2001 in an acute psychiatric inpatient unit
10. Severity of Bipolar Disorder is such that participation in a clinical trial is not appropriate because of the risk of imminent self-harm (based on clinical note review and review at screening visit by experienced clinician)
11. A history of an allergic reaction or sensitivity to Scopolamine (Hyoscine Hydrobromide). Participants will be asked at the screening visit about any previous treatment with scopolamine (Hyoscine Hydrobromide) to ascertain any previous allergic reaction or sensitivity to this agent.
12. A clinical diagnosis of narrow angle glaucoma, myasthenia gravis, paralytic ileus, pyloric stenosis, toxic megacolon and acute porphyria.
13. Individuals will be excluded from the study if currently prescribed anticholinergic medications, including Physostigmine, Biperiden and Procyclidine. Individuals will additionally be excluded if currently prescribed Tricyclic Antidepressants which are associated with significant anticholinergic properties (e.g. Amitriptyline and Nortriptyline) that are currently causing the participant to experience anticholinergic side effects (e.g. blurred vision, constipation, urinary retention, cognitive difficulties). No individuals will have anticholinergic medications stopped to allow them enter the trial.
14. Bradycardia < 50 bpm, tachycardia > 100bpm or hypotension (systolic BP <90 and / or diastolic BP < 60) prior to IV administration of placebo or Scopolamine
15. A recent history in the last 6 months of symptomatic orthostatic hypotension or syncope.
16. Previous participation in this trial. Participation is defined as randomised. Participation in another trial within 3 months prior to Visit 1. Receipt of any investigational medicinal product (IMP) within 3 months prior to Visit 1.
17. Participants concurrently being administered Electroconvulsive Therapy (ECT).
18. Pregnancy, as determined by a positive urine dipstick at Visits 2, 3, 4, 5, positive blood serum result executed at Visit 2 and confirmed prior to infusion at Visit 3 or participants who are actively breastfeeding (female only).
19. Women of child-bearing potential are defined as all women physiologically capable of becoming pregnant, unless they are using highly effective methods of contraception during dosing of study treatment. Highly effective contraception methods include:
 - Female sterilization (have had surgical bilateral oophorectomy with or without hysterectomy) or tubal ligation at least six weeks before taking study treatment.
 - Male partner sterilization
 - Combination of any two of the following:
 - a. Barrier methods of contraception e.g. Condom
 - b. Use of oral, injected or implanted hormonal methods of contraception or other forms of hormonal contraception
 - c. Placement of an intrauterine device (IUD) or intrauterine system (IUS)
 - Women who are considered post-menopausal i.e. amenorrhea at least 12 months or undergone hysterectomy/bilateral oophorectomy
20. Any disorder, unwillingness or inability, not covered by any of the other exclusion criteria, which in the investigator's opinion, might jeopardise the participant's safety or compliance with the protocol

Placebo run-in exclusion criteria at Randomisation visit (Visit 3):

21. In addition to having completed Visit 2, participants must not be experiencing a hypomanic, or manic episode (YMRS >6).
22. A Serious Adverse Event (SAE) experienced during infusion which required medical intervention and whereby attending physician deemed it inappropriate for the participant to engage in future infusions.

8.3 Recruitment, Study visits and procedures**8.3.1 Treatment duration**

Run-in period will be a maximum 21 days. The treatment period will be a maximum 10 days and the maximum number of days for follow up is 28 days

8.3.2 Identification and Recruitment

Potential participants for this study will be identified as follows:

1. Patients currently attending the Galway-Roscommon Mental Health Services, including a specialised bipolar clinic in Galway who are referred due to experiencing a depressive episode by their treating clinical team; or,
Or,
2. Patients who have previously attended NUI Galway/HRB-CRFG with an interest to participate/or have participated in research and indicated a willingness to engage in future research:
Or,
3. Patients who approach the research group directly requesting participation.

Informed written consent will be obtained prior to any study related procedures being undertaken.

8.3.3 Screening Assessments (Visit 1)

- Informed consent
- Review of inclusion/exclusion criteria
- Demographic Data (Gender, Age, Race)
- Handedness MEHI questionnaire
- Review of relevant medical and surgical history
- Review clinical history of bipolar disorder
- Recording of current medications
- Vital Signs recorded (BP, HR, RR)
- U&Es, LFTs and TFTs blood tests (if required)
- Completion of SCID-RV for DSM-V Disorders
- Completion of HDRS questionnaire
- Completion of YMRS questionnaire
- AUDIT screening for alcohol use
- Verbal confirmation received from female participants that they are not pregnant.
- Adequate contraception advice given to female and male participants (see 8.4.7)

The maximum amount of time between screening and Visit 2 will be 14 days, inclusive of weekend days and bank holidays. The screening visit and the Visit 2 may occur on the same day and thus case data for screening visit does not need to be replicated for the Visit 2.

8.3.4 Visit 2 Assessments

The following pre-treatment assessments will be performed at Visit 2.

- Confirmation of eligibility (review inclusion/exclusion criteria)
- Confirmation of pregnancy status (pregnancy tests) and contraception advice
- U&Es, LFTs and TFTs blood tests (if required)
- Review of current medications, including changes in medications since Visit 1
- Physical measurements (height and weight)
- Vital Signs recorded (BP, HR, RR) (pre-infusion but post cannulation)
- ECG to be undertaken
- Completion of HDRS (pre-infusion)
- Completion of the YMRS (pre-infusion)
- Completion by participant of the POMS (pre-infusion) (optional)
- Completion of CGI-S (pre-infusion)
- Completion of Fagerstrom (pre-infusion)
- Completion of MADRS questionnaire (pre-infusion)
- Completion by participant of a VAS (pre-infusion)
- Cannulation site check (pre-infusion)
- IV cannulation

The following post-treatment assessments will be performed at Visit 2:

- Cannulation site check (post-infusion)
- 15-minute infusion of IV placebo (100ml saline)
- Completion by participant of the POMS (minimum 15 minutes post infusion) (optional)
- Completion of WAIS (post-infusion)
- Completion of NEO (post-infusion)
- Completion by participant of a VAS (minimum 15 minutes post-infusion)
- Undertake CANTAB tests (post-infusion) (may occur at Visit 3 either)
- Vital Signs recorded (BP, HR, RR) within 15 minutes of when infusion stopped and 50 to 90 minutes post-infusion
- Completion of PRISE questionnaire by participant (post-infusion, optional)
- Assessment for other adverse effects (see section 10.1) (pre, during and post infusion)

8.3.5 Treatment (Visit 3, Visit 4 and Visit 5)

At Visit 3, after assessment, participants will be randomised to placebo (n=25) (100mls IV Saline) or 4 µg/kg Scopolamine (n=25) IV in 100mls of Saline over 15 minutes and receive further infusions at Visits 4 (days 2-6) and 5 (days 6-10), with at least 2 days between IV infusions (see Table 2).

Assessments at Visits 3 prior to randomisation to ensure trial eligibility

- As per inclusion criterion 7 and exclusion criteria 21 and 22.
- HDRS ≥ 8 (indicating depressed mood of at least mild severity)
- YMRS <6 (indicating patient is not (hypo)manic)
- Medication review to ensure no participants have been prescribed medications which would exclude the participant from the trial between Visit 2 and Randomisation.
- Confirmation of pregnancy serum result (females only)

Randomisation via Interactive Web Response System (IWRS) (Visit 3 only)

Assessments at Visits 3, 4 and 5 are:

- Review of any medication changes
- Vital Signs recorded (BP, HR, RR) (pre-infusion but post cannulation)

- Dispensing via IWRS (Visit 3, 4, and 5)
- Completion of HDRS questionnaire (Visit 3 (completed as part of eligibility assessment), Visit 4, and 5, pre-infusion)
- Completion of MADRS questionnaire (Visits 3, 4 and 5, pre-infusion)
- Completion of YMRS (Visit 3 (completed as part of eligibility assessment), Visit 4, and 5, pre-infusion)
- Confirmation of pregnancy status (Urine dipstick) and contraception advice (Visit 3, 4 and 5, pre-infusion)
- Completion by participant of VAS (Visit 3, 4, and 5, pre-infusion)
- Completion by participant of the POMS (Visit 3, 4, and 5, pre-infusion) (optional)
- Completion of GAF questionnaire (Visits 3 and 5, pre-infusion)
- Completion of CGI-S (Visit 3, 4 and 5, pre-infusion)
- Completion of CGI-I (Visits 3, 4 and 5, pre-infusion)
- IV cannulation
- Cannulation site check (pre-infusion and post-infusion)
- Completion by participant of the POMS (minimum 15 minutes post-infusion (optional)
- Completion by participant of VAS (minimum 15 minutes post-infusion)
- Completion by participant of CANTAB subscales (Visit 3, post-infusion) (optional)
- Completion of WAIS (post infusion at Visit 3, 4, or 5) (optional)
- Completion of NEOPI-FFI (post infusion at Visit 3, 4, or 5) (optional)
- Vital Signs recorded (BP, HR, RR) (within 15 minutes of infusion stopping and 50 to 90 minutes post-infusion)
- Completion by participant of the PRISE questionnaire (post-infusion at Visit 3, 4 or 5 optional)
- Assessment for other adverse effects (see section 10.1) (pre, during and post infusion)

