8.12.1.2 Secondary outcome measure

1. Remission of depressive episode after the last IV treatment (measured objectively at Visit 6), and is defined as occurring when an individual has:
 - (i) a HDRS score ≤7
 - (ii) a MADRS score <6
2. Remission of depressive episode at follow-up (measured objectively at Visit 7)
 - (i) a HDRS score ≤7
 - (ii) a MADRS score <6
3. Response to a depressive episode after the last IV treatment (measured at Visit 6) is defined as:
 - (i) a 50% reduction in MADRS score at Visit 6 compared to Visit 3

4. Response to a depressive episode at follow-up (measured objectively at Visit 7)
 - (i) a 50% reduction in MADRS score at Visit 6 compared to Visit 3
5. Improvement in mood symptoms measured with the HDRS and MADRS at visits 5, 6 and 7 compared to Visit 3.
6. Improvement in objectively measured overall functioning, measured with the GAF at Visit 5, 6 and at follow-up at Visit 7 compared to Visit 3
7. Improvement in objectively rated illness severity, measured with the CGI-S at visits 4, 5, 6 and 7 compared to Visit 3 and CGI-I at visits 4, 5, 6 and 7 compared to Visit 3.
8. Changing subjective measured depressive symptoms with the POMS and VAS
 - (i) a reduction in POMS score post-infusion compared to pre-infusion at visits 2, 3, 4 and 5 across the six different factors of the POMS (tension, depression, anger, fatigue, vigour and confusion).
 - (ii) a reduction in VAS scores post-infusion compared to pre-infusion at visits 2, 3, 4 and 5 across 8 items (happy, restless, sad, anxious, anger, drowsiness and alertness).
9. A change in subjectively measured depressive symptoms at Visit 6 compared to Visit 3 as measured with the POMS and VAS.
10. A reduction in subjectively measured depressive symptoms at follow-up (Visit 7) compared to Visit 3 as measured with the POMS and VAS.
11. Psychiatric inpatient admission of a participant due to depressive episodes between Visit 2 and Visit 7.
12. Antidepressants medication use or change by a participant due to depressive episodes over the duration of the study (Visit 2 to Visit 7):
 - (i) Introduction of a new antidepressant (yes / no)
 - (ii) Increase in dose of an existing antidepressant (yes / no)
13. Change in motor processing, visual and spatial memory (3 categorical variables) at Visit 6 compared to Visit 2 based on the CANTAB battery of tests.
14. Occurrence of a hypo (manic) episodes at visits 3, 4, 5, 6 or 7, as defined by a score of >6 on the YMRS.

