17.4.1.4 Risks and hazards secondary to IV Scopolamine infusion

AEs that have occurred have been transient in nature (<3 hours) and have included light headedness, sedation, a transiently reduced heart rate and blood pressure (requiring no intervention) and the recognised anticholinergic adverse effects of dry mouth and blurred vision (Drevets and Furey, 2010; Furey and Zarate, 2013).

Pulsed IV administration has not been associated to date with potential AEs noted with high oral dosages including delirium, (hypo)mania, psychosis or disorientation (Furey and Zarate, 2013).

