13. Change in motor processing, visual and spatial memory (3 categorical variables) at Visit 6 compared to Visit 2 based on the Cambridge Neuropsychological Test Automated Battery (CANTAB) battery of tests.

SCOPE-BD NUIG-2017-002, Statistical Analysis Plan Version 1, 19/03/2024

14. Occurrence of a hypo (manic) episodes at visits 3, 4, 5, 6 or 7, as defined by a score of >6 on the Young Mania Rating Scale (YMRS).

15. Occurrence of other adverse effects as observed on monitoring of vital signs, reported by participants or measured utilising the Patient Rated Inventory of Side Effects (PRISE) questionnaire

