### **10.2 Methods for Withdrawals, Missing Data, and Outliers**

Any missing data which occurs will be summarised and reasons given. As per the statistical analysis specification, an inverse probability weighting will be performed in the primary outcome analysis (weights based on the inverse probability of a patient's data being missing given their pre-randomisation measurements). This will ensure the estimate and inference is more representative of all patients randomised.

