## 13.2 Secondary Efficacy Analyses

Secondary outcomes will be analysed as appropriate (according to the distribution of each outcome), comparing the difference between groups at the specified follow-up visit and relative to baseline value (where specified/measured). Baseline variables predictive of each outcome (the measure at baseline where available), and stratifying

SCOPE-BD NUIG-2017-002, Statistical Analysis Plan Version 1, 19/03/2024  
variables will be included in ANCOVA or generalised linear models of outcome variables.

For secondary outcomes, the focus will be on the point estimates and confidence intervals for hypothesis generation.

Additional analysis of the primary outcome will compare the time course of HDRS under placebo and treatment using a mixed-effects model including fixed-effects terms for time since randomisation/study visit, trial arm and their interactions, and a random effect to account for correlation of multiple observations per participant.

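### The CANTAB baseline is defined in two incompatible ways, and one of them accepts a score taken after the first randomised infusion

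*Protocol*

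**What the plan says.** **Timing of the test.** Protocol 8.3.4 schedules CANTAB after the Visit 2 infusion, which is saline for every participant, and allows it to be deferred: "Undertake CANTAB tests (post-infusion) (may occur at Visit 3 either". Protocol 8.3.5 places the Visit 3 test after that visit's infusion: "Completion by participant of CANTAB subscales (Visit 3, post-infusion) (optional". Randomisation happens earlier in the same visit, so this infusion is the first randomised one. Neither visit list contains a pre-infusion CANTAB at Visit 3.

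**Definition of baseline.**
- Protocol 7.3.2 item 15 compares Visit 6 with either visit: "compared to initial scores measured at Visit 2 or Visit 3 as measured on CANTAB".
- Protocol 8.12.1.2 item 13 uses Visit 2 only: "3 categorical variables) at Visit 6 compared to Visit 2 based on the CANTAB battery of tests".
- SAP 5.2.2 item 13 does the same: "at Visit 6 compared to Visit 2 based on the Cambridge Neuropsychological Test Automated Battery".

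**Analysis rules.** SAP 5.3 derives change scores from the endpoint definitions. SAP 13.2 adjusts for "the measure at baseline where available". SAP 10.2 confines the missing-data method to the primary endpoint: "an inverse probability weighting will be performed in the primary outcome analysis".

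**The concern.** A baseline has to be measured before randomised treatment can act on it. The Visit 3 CANTAB score is not. The Visit 2 score also follows an infusion, but a saline one in both arms, so it cannot differ by arm.

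The two definitions fail in different ways for a patient first tested at Visit 3:
- Under Protocol 7.3.2, a scopolamine patient's baseline is measured on drug and a placebo patient's is not. If the drug impairs performance acutely, simple recovery by Visit 6 looks like cognitive improvement in the active arm.
- Under the SAP, the patient has no usable baseline, and nothing says whether the patient is dropped, compared at Visit 6 without one, or given the Visit 3 score instead.

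The protocol itself makes an acute effect plausible. Section 6.2.1 gives M1 and M3 receptors a part in cognitive function. Exclusion criterion 13 counts cognitive difficulties and blurred vision among anticholinergic side effects. Section 10.2.1.2 expects drowsiness and blurred vision in the 90 minutes after infusion. Section 17.4.1.4 says "AEs that have occurred have been transient in nature (<3 hours) and have included light headedness, sedation".

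Cognition is part of the first secondary objective, and the synopsis names cognitive change at Visit 6 among the secondary endpoints.

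**Working it through.** The contradiction itself needs no arithmetic. The plan states no CANTAB figure to reproduce. The calculations below only show how large the consequence could be.

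**Side by side, for a patient first tested at Visit 3**

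| Rule | Baseline used | Result |
|---|---|---|
| Protocol 7.3.2 item 15 | Visit 3, after the randomised infusion | On drug in the scopolamine arm, off drug in the placebo arm |
| Protocol 8.12.1.2 item 13; SAP 5.2.2 item 13 | Visit 2 | None exists; handling not stated |

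**Inputs from the documents.** Half-life about 3 hours (Protocol 6.2.3); minimum stay 90 minutes after infusion (Protocol 8.4.4.1); 44 evaluable patients, 22 per arm (Protocol 11.2, SAP 7). The 44 is the HDRS follow-up figure, borrowed here because no CANTAB denominator is given.

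**Assumed inputs, not in the documents.** Share first tested at Visit 3, f = 0.1 to 0.4; acute decrement, d = 0.2 to 0.5 SD; test–retest correlation 0.7; no true effect; scores treated as continuous with SD 1.

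**Step 1: drug still present.** With single-exponential elimination, the fraction remaining is 0.5^(t/3 h).
- At 15 minutes: 0.5^(0.25/3) = 0.944.
- At 90 minutes: 0.5^(1.5/3) = 0.707.

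A test taken during the required stay is therefore taken with most of the drug still in plasma. No delay between infusion and CANTAB is specified; 15 minutes is only an example.

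**Step 2: SAP rule, if patients without a baseline drop out of the change comparison.** Lost baselines = 44 × f. Standard-error multiplier = 1/√(1 − f).
- f = 0.1: 4.4 patients; 1.05.
- f = 0.2: 8.8 patients; 1.12.
- f = 0.4: 17.6 patients; 1.29.

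**Step 3: Protocol 7.3.2 rule.** A fraction f of active-arm baselines is lowered by d.
- Bias on the change score = f × d.
- Bias under ANCOVA = f × d × 0.7 / (1 + f(1 − f)d²/2).
- SD of a change score in placebo = √(2 × (1 − 0.7)) = 0.775.
- Share gaining more than 0.5 SD (an illustrative cut-off) in placebo = P(Z > 0.5/0.775) = 25.9%. In the active arm it is (1 − f) × 25.9% + f × P(Z > (0.5 − d)/0.775).
- The last column is the chance that a two-sample t interval on change, 22 per arm, excludes zero.

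| f, d | Change bias (SD) | ANCOVA bias (SD) | Active arm gaining > 0.5 SD (placebo 25.9%) | 95% CI excludes zero (nominal 5%) |
|---|---|---|---|---|
| 0.1, 0.2 | 0.020 | 0.014 | 26.8% | 5.1% |
| 0.2, 0.5 | 0.100 | 0.069 | 30.7% | 7.0% |
| 0.4, 0.5 | 0.200 | 0.136 | 35.6% | 12.9% |

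A simulation with 1,000,000 patients per arm gave 0.019 and 0.014 for the first row, and 0.200 and 0.137 for the last. A separate calculation with wider assumptions (share 10–50%, decrement 0.3–1.0 SD, correlation 0.6–0.8) gave 0.03–0.50 SD on change and about 0.02–0.36 SD under ANCOVA. The direction is the same; the size follows the inputs.

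**The case against.** The strongest reply is that the analysis document has already chosen. SAP Version 1 (March 2024) is later than Protocol Version 3 (December 2020). It names Visit 2, agrees with Protocol 8.12.1.2, and ties change scores to its own endpoint list. An analyst who follows it never uses a post-dose baseline, so the bias in Step 3 arises only by departing from the SAP. This stands, and the Step 3 figures are conditional on using 7.3.2. It does not remove the problem: the protocol still permits the deferral, and the SAP rule then leaves those patients without a baseline.

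A second reply is that SAP 13.2 foresees unmeasured baselines, because it compares groups relative to baseline only where one was specified or measured. That wording can be read as allowing a Visit 6 comparison without a baseline. It is too general to settle how a patient with only a post-dose Visit 3 score enters a change endpoint, and Step 2 applies only if such patients are dropped.

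A third reply is that the magnitude rests on assumptions. This also stands. The share deferred, the decrement and the correlation are not in the documents. CANTAB is optional, and Visit 6 may be done by telephone, so the true denominator may be below 44. The endpoint is described as three categorical variables, so the SD-scale results are only a guide.

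Finally, the stakes are limited: CANTAB is one of fifteen secondary outcomes, all exploratory under SAP 10.5.

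**Conclusion.** The concern holds. The protocol gives two incompatible CANTAB baselines. One accepts a score that the visit schedule places after the first randomised dose; the other, which the SAP follows, leaves patients first tested at Visit 3 without a baseline or a handling rule.

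The size cannot be determined from the documents. Under the stated assumptions it runs from negligible to a false benefit of 0.20 SD on change (0.14 SD under ANCOVA) if 7.3.2 is followed, or a standard error 1.05 to 1.29 times larger if the SAP is followed and those patients are dropped. The primary HDRS analysis is untouched. This should be corrected, but it does not threaten the trial's main conclusion.

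**What to change.** 1. In Protocol 7.3.2 item 15, Protocol 8.12.1.2 item 13 and SAP 5.2.2 item 13, define the CANTAB baseline as the last score before the first randomised infusion. For everyone tested at Visit 2 only, this is the SAP's present rule.
2. In Protocol 8.3.4 and 8.3.5, move any Visit 3 CANTAB to before the infusion.
3. State in the SAP that post-infusion Visit 3 scores are never used as baseline.
4. State in the SAP that patients without a pre-dose score stay in the Visit 6 between-arm comparison, with the baseline covariate treated as missing. One acceptable method is a single value chosen without regard to arm plus a missing indicator for a continuous score, or a not-tested level for a categorical one. Whether the Visit 2 test was deferred is settled before randomisation, so this missingness does not depend on arm.

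**Cost.** Items 3 and 4 and the SAP part of item 1 are wording. The protocol changes need a small amendment, reviewed by the competent authority and ethics committee under Protocol 15.1. Visit 3 takes longer before dosing, and optional scores already collected after the Visit 3 infusion are lost as baselines. If few patients remain to be enrolled, most of the gain comes from the SAP wording.
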